Appendix I: CHRONIC KIDNEY DISEASE (CKD) HYPERTENSION MANAGEMENT PROTOCOL

This protocol will be initiated as directed by CHRONIC KIDNEY DISEASE (CKD) CHRONIC DISEASE MANAGEMENT PROTOCOL.

Protocol will be reviewed every year.

RN will perform protocol with assistance from PA or NP at same clinical site.

PA or NP may suggest deviations from protocol as deemed clinically appropriate.

Orders (except medication orders) will be placed by RN in electronic medical record using "per protocol" order mode with physician, PA or NP as authorizing provider. Medication orders may be routed to provider as suggested per protocol, but medication and dose will ultimately be selected and ordered by provider. After medication orders are finalized by provider, RN will notify patient of final decision.

Goals/Background

1. Chronic Kidney Disease (CKD) is defined as (for the purposes of this protocol):
 - a. Glomerular Filtration Rate (GFR) < 60 mL/min
 - b. Or presence of proteinuria, defined as any one of the following:
 - i. Random Urine Protein/Creatinine Ratio > 200 mg/g
 - ii. Random Urine Microalbumin/Creatinine Ratio > 30 mg/g
 - iii. 24 hour Urine Protein > 150mg
 - iv. Urine dipstick protein (adjusted for specific gravity)
2. Blood pressure (BP) goals
 - a. For patients with CKD goal blood pressure is Systolic (SBP) < 140 mmHg AND Diastolic (DBP) < 90 mmHg
3. ACEi/ARB
 - a. All patients with chronic kidney disease (with or without proteinuria) should be treated with an angiotensin converting enzyme inhibitor (ACEi) or angiotensin receptor blocker (ARB).
 - b. Recommended ACEi: lisinopril
 - i. Starting dose 5mg once daily if GFR > 10 mL/min or 2.5mg if GFR < 10mL/min
 - ii. Maximum dose 40mg once daily
 - iii. Class-specific considerations. Be aware of these potential adverse effects when conduction follow-up of initiation or titration of this medication (details on the follow-up process are below).
 1. Elevated potassium (hyperkalemia)
 2. Reduction in kidney function (increase in creatinine or decrease in GFR)
 3. Dry cough

- 4. Facial swelling (angioedema)
- c. Recommended ARB: losartan
 - i. Starting dose 25mg once daily
 - ii. Maximum dose 100mg once daily
 - iii. Class-specific considerations. Be aware of these potential adverse effects when conduction follow-up of initiation or titration of this medication (details on the follow-up process are below).
 - 1. Hyperkalemia

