 - 3. If difference < 10 mmHg (systolic or diastolic), under CKD diagnosis in Problem List, record in Overview section: "Home BP Device Validation [DATE]: home device validated as consistent with RN measurement" and proceed to "Home Blood Pressure Log Review".

5. Home Blood Pressure Log Review

- a If BP cuff is validated as above and home BP log is used in clinical decision-making, log should be scanned into Epic.
- b Calculate average of seven most recent systolic and diastolic values (i.e. sum of seven most recent systolic values divided by 7; and sum of seven most recent diastolic values divided by 7).
- c If average systolic > 140 mmHg or average diastolic > 90 mmHg, initiate CKD HYPERTENSION PROTOCOL and perform at this visit.
- d If average systolic < 140 mmHg AND average diastolic < 90 mmHg, no further action is necessary.
- e Consider extenuating circumstances such as acute pain and acute psychological distress. Discuss with provider if you feel such extenuating circumstances are contributing to blood pressure elevation. Consider rescheduling RN BP Assessment Visit in 2-4 weeks to reassess.

- f Assess for adverse effects every visit including class-specific considerations above as well as side effects common to many blood pressure medications which include (but are not limited to) lightheadedness and fainting.
 - (i) If any new adverse effects, discuss with provider.
 - (ii) If no new adverse effects, proceed to BP Medication Adherence Assessment.
- g BP Medication Adherence Assessment
 - (i) Ask patient about each BP medication and ask, "How many days per week do you forget your [insert BP medication]?"
 - (ii) If one day or less, consider adherent by self-report.
 - (iii) Review BP medication bottles if available.
 - (iv) If medications are filled at Parkland pharmacy, review refill history in Cerner for last 6 months. Consider adherent if obtains within 6 days for a 30 day prescription or within 18 days for a 90 day prescription.
 - (v) If not adherent by self-report or refill history, discuss with patient importance of adherence.
 - (a.) Reschedule RN BP Assessment Visit in 2 weeks after improved adherence.
 - (b.) If patient was deemed non-adherent on two consecutive visits, refer to clinical pharmacist for medication review and assistance with barriers to adherence (cost, complexity, etc).
 - (vi) If considered adherent by self-report and refill history, proceed to "Medication Adjustment".

6. Medication Adjustment

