- ii. For patients with GFR < 30, recommend furosemide.
 - 1. Starting dose 20mg twice daily.
 - a. Maximum dose dependent on provider assessment of volume status. All follow-up evaluations should be discussed with provider.
- iii. Class-specific considerations
 - 1. Must counsel patients that diuretics will increase urinary frequency
 - 2. May worsen prostate symptoms in men.
- c. If patient is already on maximum tolerated diuretic and no history of myocardial infarction or heart failure, recommend CALCIUM CHANNEL BLOCKER PROTOCOL.
 - i. For patients with proteinuria, recommend non-dihydropyridine calcium channel blocker (CCB) verapamil SR as it may help reduce proteinuria.
 - 1. Recommended starting dose verapamil SR 120mg once daily.
 - 2. Maximum dose verapamil SR 360mg once daily.
 - ii. For patients without proteinuria, dihydropyridine CCB amlodipine may be used.
 - 1. Recommended starting dose amlodipine 5mg once daily.
 - 2. Maximum dose amlodipine 10mg once daily.
 - iii. Class-specific considerations
 - 1. Amlodipine may cause increased heart rate (reflex tachycardia).
 - 2. Verapamil may cause bradycardia and constipation.

Both may cause lower extremity swelling.
- d. If patient is already on maximum tolerated doses of beta-blocker, diuretic and calcium channel blocker, recommend HYDRALAZINE PROTOCOL.
 - i. Hydralazine
 - 1. Recommended starting dose 10mg three times daily.
 - 2. Maximum dose 100mg three times daily.
 - iii. Class-specific considerations
 - 1. May cause reflex tachycardia.
- e. If patient is already on maximum tolerated doses of beta-blocker, diuretic and calcium channel blocker and hydralazine, discuss with provider the following:
 - i. Referral to Hypertension Clinic.
 - ii. Referral to clinical pharmacist for full medication review and assessment of adherence.
 - iii. Return management of hypertension to PCP for work-up of secondary hypertension and selection of fifth anti-hypertensive agent.

BETA-BLOCKER PROTOCOL

1. Discuss following medication suggestions with provider. These are only suggestions to guide management, but final selection is at provider's discretion.
2. Perform RN BP Assessment as detailed above.
3. Is BP at goal?
 - a. Yes. Continue regimen and schedule RN BP Assessment Visit in 3 months and follow-up with PCP within 6 months.
 - i. If BP continues to be at goal in 3 months, can return hypertension management to PCP.

- b. No 4 is HR > 60?

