 - i. Yes. Route pended order to provider for carvedilol 6.25mg twice daily (or alternative beta-blocker as directed by provider) and schedule for "Follow-Up" as detailed below in 2-4 weeks.
 - ii. No. Discuss with provider safety of starting beta-blocker or alternatively selection of diuretic, calcium channel blocker or hydralazine protocols.
- 4. Follow-Up
 - a. Perform RN BP Assessment as detailed above in 2-4 weeks.
 - b. Is BP at goal?
 - i. Yes. Continue regimen and schedule RN **BP** Assessment Visit in 3 months and follow-up with PCP within 6 months.
 - 1. If BP continues to be at goal in 3 months, can return hypertension management to PCP.
 - ii. No. Is HR > 60?
 - 1. Yes. Is beta-blocker at maximum dose?
 - a. No. Route pended order to provider for double prior dose of beta-blocker and schedule for "Follow-Up" as detailed above in 2-4 weeks.
 - b. Yes. Return to NON-ACEi/ARB PROTOCOL for selection of next medication.
 - 2. No. Discuss with provider safety of continuing beta-blocker or selection of diuretic, calcium channel blocker or hydralazine protocols.

DIURETIC PROTOCOL

- 1. Discuss following medication suggestions with provider. These are only suggestions to guide management, but final selection is at provider's discretion.
- 2. Perform RN BP Assessment as detailed above.
- 3. Is BP at goal?
 - a. Yes. Continue regimen and schedule RN BP Assessment Visit in 3 months and follow-up with PCP within 6 months.
 - i. If BP continues to be at goal in 3 months, can return hypertension management to PCP.
 - b. No. Proceed with diuretic selection
- 4. Diuretic selection
 - a. If no K or GFR in last three months then order POTASSIUM LEVEL and CREATININE WITH eGFR in EHR.
 - i. Is K > 3.5?
 - 1. No. Discuss with provider safety of initiation or titration of diuretic or need for potassium supplementation and schedule for "Follow-Up" as detailed below in 2-4 weeks after provider has provided recommendation.
 - 2. Yes. Is patient already taking diuretic?
 - a. Yes. Discuss with provider next choice (consider recommendations below based on GFR) and schedule for "Follow-Up" as detailed below in 2-4 weeks.

- b. No. Is GFR > 30?
 - (i) Yes. Recommend thiazide diuretic such as chlorthalidone 12.5mg or other diuretic selected by provider and schedule for "Follow-Up" as detailed below in 2-4 weeks.
 - (ii) No. Recommend furosemide 20mg twice daily or other diuretic selected by provider and schedule for "Follow-Up" as detailed below in 2-4 weeks.

5. Follow-Up

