
- a. Schedule RN BP Assessment Visit in 2-4 weeks
- b. Order POTASSIUM LEVEL and CREATININE WITH E-GFR and request patient have labs drawn at least 1 business day prior to visit.
- c. Perform RN BP Assessment as detailed above in 2-4 weeks.
- d. Is K > 3.4?
 - i. No. Discuss with provider change in therapy or potassium supplementation. Discuss follow up plan for K with provider as well.
 - ii. Yes
 - 1. Is GFR > 10% lower than last value?
 - a Yes. Discuss with provider decrease in diuretic dose or stopping diuretic. Discuss follow up plan for Cr with provider as well.
 - b No. Is BP at goal?
 - (i) If BP is still not at goal at maximum tolerated dose of diuretic, return to NON-ACEi/ARB PROTOCOL.
 - (ii) If BP is still not at goal and not taking chlorthalidone 25mg or maximum tolerated dose of diuretic, then discuss with provider if dose of diuretic should be increased.
 - (iii) If provider recommends to increase dose, schedule for "Follow-Up" as detailed above in 2-4 weeks.
 - (iv) If provider recommends to not increase dose, return to NON-ACEi/ARB PROTOCOL.

CALCIUM CHANNEL BLOCKER PROTOCOL

1. Discuss following medication suggestions with provider. These are only suggestions to guide management, but final selection is at provider's discretion.
2. Perform RN BP Assessment as detailed above.
3. Is BP at goal?
 - a. Yes. Continue regimen and schedule RN BP Assessment Visit in 3 months and follow-up with PCP within 6 months.
 - i. If BP continues to be at goal in 3 months, can return hypertension management to PCP.
 - b. No. Is patient already taking calcium channel blocker (CCB)?
 - i. Yes - Is CCB at maximum dose?
 - 1 Yes. Return to NON-ACEi/ARB PROTOCOL.
 - 2 No. Route pended order to provider for double dose of current CCB and schedule for "Follow-Up" as detailed below in 2-4 weeks.
 - a No. Does patient have proteinuria as defined above?
 - b Yes. Route pended order for verapamil SR 120mg once daily and

proceed to "Follow-Up" below.

c No. Route pended order for amlodipine 5mg once daily and schedule for "Follow-Up" as detailed below in 2-4 weeks.

4. Follow-Up

- Perform RN BP Assessment as detailed above in 2-4 weeks.
- Is HR ≥ 100 ?
 - Yes - discuss with provider
 - No. Is BP at goal?
 - Yes. Continue regimen and schedule RN BP Assessment Visit in 3 months and follow-up with PCP within 6 months.
 - If BP continues to be at goal in 3 months, can return hypertension management to PCP.
 - No. Is CCB at maximum dose?

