 - No. Route pended order to provider for double dose of current CCB and return to follow-up above.
 - Yes. Return to NON-ACE i/ARB PROTOCOL.

HYDRALAZINE PROTOCOL

- Discuss following medication suggestions with provider. These are only suggestions to guide management, but final selection is at provider's discretion.
- Perform RN BP Assessment as detailed above.
- Is BP at goal?
 - Yes. Continue regimen and schedule RN BP Assessment Visit in 3 months and follow-up with PCP within 6 months.
 - If BP continues to be at goal in 3 months, can return hypertension management to PCP.
 - No. Route pended order to provider for hydralazine 10mg PO TID. If patient is already taking hydralazine 10mg PO TID, route pended order to provider for dose to 25mg PO TID. If patient is already taking 25mg or more TID, route pended order to provider for double current dose of hydralazine if not at maximum dose. Schedule for "Follow-Up" as detailed below in 2-4 weeks.
- Follow-Up
 - Perform RN BP Assessment as detailed above in 2-4 weeks.
 - is HR > 100 ?
 - Yes. Discuss with provider
 - No. Is BP at goal?
 - Yes. Continue regimen and schedule RN BP Assessment Visit in 3 months and follow-up with PCP within 6 months.
 - If BP continues to be at goal in 3 months, can return hypertension management to PCP.
 - No. Is hydralazine at maximum dose?
 - No. Route pended order to provider for double current dose of hydralazine and return to follow-up above.
 - Yes. Return to NON-ACEi/ARB PROTOCOL.

References

James PA et al. 2014 Evidence-based Guideline for the Management of High Blood Pressure in Adults. Report from the Panel Members Appointed to the Eighth Joint National Committee (JNC 8). *JAMA* 2014, 311(5):507-520

Kidney Disease: Improving Global Outcomes (KDIGO) CKD Work Group. KDIGO 2012 Clinical Practice Guideline for the Evaluation and Management of Chronic Kidney Disease. *Kidney International* 2013, Supp 3:1-150

Kidney Disease: Improving Global Outcomes (KDIGO) Blood Pressure Work Group. KDIGO Clinical Practice Guideline for the Management of Blood Pressure in Chronic Kidney Disease. *Kidney International* 2012, Supp 2:337-414

K/DOQI Clinical Practice Guidelines for Chronic Kidney Disease: Evaluation, Classification and Stratification. *Am J Kidney Dis* 2002, 39: S266.

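### The calcium channel blocker Follow-Up sets no explicit low heart-rate question or threshold before verapamil is doubled, and its doubling rule overshoots the stated verapamil maximum

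*Combined protocol and SAP*

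**What the plan says.** Appendix I, NON ACEi/ARB PROTOCOL, item c, offers two CCBs with opposite heart-rate risks. Amlodipine is listed with reflex tachycardia. For the other drug the text says "Verapamil may cause bradycardia and constipation". Verapamil SR is suggested when there is proteinuria and amlodipine when there is not. Verapamil starts at 120 mg once daily, and the ceiling is given as "Maximum dose verapamil SR 360mg once daily".

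The CALCIUM CHANNEL BLOCKER PROTOCOL has three points at which verapamil can be started or raised:

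- **Start (step 3.b):** 120 mg is queued if there is proteinuria. No heart-rate question.
- **Already on a CCB below maximum (step 3.b):** "No. Route pended order to provider for double dose of current CCB and schedule for" a Follow-Up in 2-4 weeks. No heart-rate question.
- **Follow-Up (step 4):** the nurse repeats the RN BP Assessment, then asks whether heart rate is at least 100, whether blood pressure is at goal, and whether the CCB is at maximum. Three negative answers lead to "Route pended order to provider for double dose of current CCB and return to follow-up above".

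Three safeguards surround these steps. The introduction to Appendix I states: "Medication orders may be routed to provider as suggested per protocol, but medication and dose will ultimately be selected and ordered by provider". The RN BP Assessment tells the nurse: "Assess for adverse effects every visit including class-specific considerations above as well as side effects common to many blood pressure medications", and any new effect goes to the provider. Step 1 of the CCB protocol, which precedes the start and the step 3.b doubling, says: "Discuss following medication suggestions with provider. These are only suggestions to guide management".

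The BETA-BLOCKER PROTOCOL asks whether heart rate exceeds 60 before the first order and again before each doubling. At its Follow-Up, a negative answer leads to: "Discuss with provider safety of continuing beta-blocker or selection of diuretic, calcium channel blocker or hydralazine protocols".

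**The concern.** The heart-rate questions in the beta-blocker and hydralazine protocols match the risks named for those drugs: a slow rate for the first, a fast rate for the second. The CCB question matches only one of its two drugs. For verapamil it tests the direction that the appendix does not warn about and leaves the direction that it does warn about without a question. On the numbered branches, a patient whose rate has slowed on verapamil is routed to a larger dose.

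The same step raises a second, independent matter. It tests whether the current dose is below maximum, not whether the doubled dose would be, so it can queue an order above the ceiling printed in the same appendix.

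What is at stake is the safety of titration in the intervention arm. The estimate of the primary outcome is not in question.

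**Working it through.** The plan states no figure to reproduce. The check is a trace of the written steps, followed by dose arithmetic.

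**1. Heart-rate questions against named risks (Appendix I)**

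| Protocol | Heart-rate risk named | Question before start | Question before Follow-Up doubling |
|---|---|---|---|
| Beta-blocker | bradycardia | HR > 60 | HR > 60 |
| Hydralazine | reflex tachycardia | none | HR > 100 |
| CCB, amlodipine | reflex tachycardia | none | HR ≥ 100 |
| CCB, verapamil | bradycardia | none | HR ≥ 100 (wrong direction) |

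**2. Trace of an assumed patient.** Verapamil SR 120 mg, adherent, no symptoms, HR 48, BP 150/84 (goal: below 140 and below 90).

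- Follow-Up step a: RN BP Assessment, including the adverse-effect check. If the nurse recognises 48 as bradycardia, it goes to the provider. If not, the trace continues.
- HR ≥ 100? 48 < 100, so No.
- BP at goal? 150 ≥ 140, so No.
- CCB at maximum? 120 < 360, so No.
- Result: a doubled order, 240 mg, is queued.

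In the beta-blocker Follow-Up, 48 is not above 60, so the written result is a provider discussion and no queued order.

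**3. Timing and dose.** Assume that the provider signs 240 mg and that rate and pressure stay as above. Each Follow-Up comes after 2-4 weeks.

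- First Follow-Up (2-4 weeks after the start): 2 × 120 = 240 mg queued.
- Second Follow-Up (4-8 weeks): 240 < 360, so the maximum has not been reached, and 2 × 240 = 480 mg is queued.
- Excess: 480 − 360 = 120 mg, and 120/360 = 33%.

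**4. Is this peculiar to verapamil?** Doubling lands exactly on the maximum only when maximum ÷ starting dose is a power of 2.

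| Drug (mg per dose) | Max ÷ start | Doubling sequence | Excess |
|---|---|---|---|
| Amlodipine | 10/5 = 2 | 5, 10 | 0 |
| Carvedilol | 25/6.25 = 4 | 6.25, 12.5, 25 | 0 |
| Losartan | 100/25 = 4 | 25, 50, 100 | 0 |
| Lisinopril | 40/5 = 8 | 5, 10, 20, 40 | 0 |
| Verapamil SR | 360/120 = 3 | 120, 240, 480 | 120 |
| Hydralazine, Follow-Up step only | 100/10 = 10 | 10, 20, 40, 80, 160 | 60 |
| Hydralazine, step 3.b | 10 to 25, then 100/25 = 4 | 10, 25, 50, 100 | 0 |

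The rule fails for verapamil, and for hydralazine when the Follow-Up loop alone is used from 10 mg.

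**The case against.** The strongest reply is that a slow rate is not ignored. Every CCB Follow-Up opens with the RN BP Assessment, and its adverse-effect check runs at every visit. Bradycardia is a sign, so the absence of symptoms does not bypass the check, and the nurse already has the rate in hand. The order is only queued: the provider chooses drug and dose, a PA or NP may suggest departures, and activating the protocols is optional for the practitioner (section 6.5). Syncope and hypotension are captured safety events (section 9.1).

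All of this stands. A reader might infer that verapamil is doubled with no low-rate prompt of any kind. The documents do not support that. Read literally, the word *above* in the adverse-effect item reaches only the ACEi/ARB lists printed before it. But the assessment is a module called from each later drug protocol, and at the CCB call the CCB list is above. The narrow reading would leave those later lists without a use at nurse follow-up. The wider reading, which includes verapamil's bradycardia, is the reasonable one.

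A reader might also infer that patients would take 480 mg. That would need the provider to sign 240 mg, the nurse to queue a dose above a printed maximum, and the provider to sign that too.

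The reply does not explain why verapamil differs from the beta-blocker. Sign-off and the adverse-effect check cover both protocols, yet the authors wrote a low-rate threshold for one only. The check that remains for verapamil carries no number.

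It is also fair to say that the dose overshoot has nothing to do with heart rate. It is reported here as a separate defect and does not measure the heart-rate gap.

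**Conclusion.** The point holds in limited form. The CCB protocol lacks an explicit nurse-level low-rate question or threshold for verapamil; it does not lack all safety review. The gap is clearest at the Follow-Up doubling, because the start and the step 3.b doubling come after the provider discussion in step 1. The heart-rate gap cannot be sized: the documents do not say how many patients would take verapamil or have a slow rate.

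The dose overshoot is firm arithmetic: a queued order of 480 mg against 360 mg (33% over), and for hydralazine 160 mg against 100 mg by the Follow-Up loop. It rests on the steps being followed as written, with each earlier order signed and pressure still above goal.

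Reach is limited. The recommended route to verapamil is a patient with proteinuria, already on the highest diuretic dose tolerated, without a past infarction or heart failure. It normally follows ACEi/ARB titration, but patients for whom both are contraindicated also enter. One further route matters: a provider may choose the CCB protocol for a beta-blocker patient whose rate is not above 60, and no later CCB step repeats the low-rate question.

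This merits correction as a titration-safety edit. Nothing here bears on the primary outcome, the sample size or the analysis.

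**What to change.** In Appendix I:

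1. **Low-rate question for verapamil.** Add it before the Follow-Up doubling first, then before the step 3.b doubling and the start order. HR > 60, as in the beta-blocker protocol, is an example; the sponsor's clinicians should set the threshold, since that figure comes from another drug class. If it is not met, queue no order and discuss with the provider.
2. **Keep HR ≥ 100 for amlodipine.**
3. **Cap the queued dose.** In the CCB and hydralazine Follow-Up steps, limit the doubled dose to the stated maximum. The verapamil sequence becomes 120, 240, 360 mg, and hydralazine from 10 mg ends 80, 100 mg. The same phrase suits CCB step 3.b, which uses the same doubling rule.

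The cost is a few lines in an appendix that is already reviewed yearly, and a few more provider discussions. Heart rate is already asked at CCB Follow-Up, so the main change needs no new reading; the start and step 3.b would need one. Any site order set that encodes these steps would have to be matched. The documents do not show that content, so that effort cannot be judged here.
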